### 2.1 PRIMARY OBJECTIVE AND ENDPOINT

Objective	Endpoint
Determine the efficacy of four doses of VGX-3100, alone or in combination with imiquimod, with respect to combined histopathologic regression of vulvar HSIL and virologic clearance of HPV-16/18 in vulvar tissue	Proportion of subjects with no histologic evidence of vulvar HSIL and no evidence of HPV-16/18 at Week 48 in vulvar tissue samples (i.e. collected via biopsy or excisional treatment).

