7. Describe association of microRNA (miRNA) profile, previous vulvoscopy, and HPV testing results with Week 48 histologic regression	7. Vulvoscopy, HPV test results (vulvar swab and vulvar tissue) and miRNA profile (Day 0, Week 15 and 48) in conjunction with histologic regression of vulvar HSIL at Week 48 visit
8. Describe patient reported outcomes (PRO) for subjects treated with VGX-3100 and VGX-3100 with imiquimod	8. PRO endpoints will be obtained at Day 0 prior to first dose, Weeks 4, 12, 24 after dosing, and at Weeks 15, 27, 48, 52, 74, 96 and 100.

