### 3.2.1 DEFINITION OF RESPONDER AND NON-RESPONDER

A treatment responder is defined as a subject with no histologic evidence of vulvar HSIL and no evidence of HPV-16 or HPV-18 in vulvar tissue at evaluation and who did not receive any non-study related treatment for vulvar HSIL. A treatment non-responder is a subject with histologic evidence of vulvar HSIL or vulvar carcinoma at evaluation, or a subject with evidence of HPV-16/18 at evaluation, or a subject who received non-study related treatment for vulvar HSIL. Any case of histologically confirmed progression is considered a non-responder. Progression is defined as advancement to carcinoma by histology according to the PAC.

Responder and non-responder definitions (Table 3) take into account both histopathologic regression of vulvar HSIL and virologic (HPV-16/18) clearance from tissue samples since HPV persistence is an important factor in the clinical progression of HSIL.

Table 3: Definition of Responder and Non-responder	
Responder	Non-Responder
Subject with no histologic evidence of vulvar HSIL AND Subject with no evidence of HPV-16 or HPV-18 in vulvar tissue at evaluation AND Subject who did not receive any non-study related treatment for vulvar HSIL	Subject with histologic evidence of vulvar HSIL or vulvar carcinoma at evaluation OR Subject with evidence of HPV-16 or HPV-18 in vulvar tissue at evaluation OR Subject who received non-study related treatment for vulvar HSIL

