## 8.9 EFFICACY ANALYSIS

The true treatment effect on the primary endpoint is  $p$ , where  $p$  denotes the true population probability of the primary endpoint for each arm. The primary hypothesis of superiority is:

$H_0: p \leq 0.02$  vs.  $H_1: p > 0.02$ , for each treatment arm separately.

A p-value for these hypothesis tests and corresponding 95% confidence intervals will be computed based on the exact method of Clopper-Pearson. Superiority will be concluded if the one-sided p-value is  $< 0.025$  and the corresponding lower bound of the 95% CI exceeds 0.02.

The secondary efficacy binary endpoints will be analyzed in the same manner as the primary hypothesis, but without the hypothesis test p-values.

For the analyses, the efficacy time frame is defined by any time starting from 14 days prior to the -specified visit week.

The anatomic extent endpoint will be analyzed by calculating the mean percent change and associated 95% t-distribution based confidence interval. The percentage of subjects with no clinically significant lesion resolution (reduction in lesion size of 25% or less), partial lesion resolution (26-99% reduction), and complete reduction (100% reduction) will be summarized with point estimates and associated exact Clopper-Pearson 95% confidence intervals.

An exploratory analysis will examine clearance outside of the vulva. This will be analyzed in the same manner as vulvar clearance.

An exploratory analysis will examine the relationship between the primary efficacy endpoint and a) HLA results, b) miRNA results, c) vulvoscopy results, and d) HPV results. Relationships will be examined with contingency tables and/or logistic regression models which model the primary endpoint versus these results and treatment group as regressor variables.

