**Study Population:**

Inclusion:

1. Must understand, agree and be able to comply with the requirements of the protocol. Subjects must be willing and able to provide voluntary consent to participate and sign a Consent Form prior to study-related activities;
2. Women aged 18 and above
3. Vulvar infection with HPV types 16 and/or 18 confirmed by screening biopsy;
4. Vulvar tissue specimen/blocks must be collected within 10 weeks prior to anticipated date of first dose of study drug and have histologically confirmed vulvar HSIL by the Pathology Adjudication Committee at screening;
5. Must be judged by the Investigator to be an appropriate candidate for the protocol-specified procedure (i.e. excision or biopsy) required at Week 48;
6. Must have vulvar HSIL that is accessible for sampling by biopsy instrument and of adequate size to ensure that a visible lesion remains after an approximately 4 mm screening biopsy;
7. Must have vulvar HSIL that can be completely demarcated for area measurement;
8. Must meet one of the following criteria with respect to their reproductive capacity:
  - a) Is post-menopausal as defined by spontaneous amenorrhea for more than 12 months or spontaneous amenorrhea for 6-12 months with FSH level >40 mIU/mL;
  - b) Is surgically sterile due to absence of ovaries or due to a bilateral tubal ligation/occlusion performed more than 3 months prior to screening;
  - c) Women of Child Bearing Potential (WOCBP) are willing to use a contraceptive method with failure rate of less than 1% per year when used consistently and correctly from screening until 6 months following the last dose of investigational product. Acceptable methods are the following:
    - i) Hormonal contraception: either combined or progestin-alone including oral contraceptives, injectable, implants, vaginal ring, or percutaneous patches. Hormonal contraceptives must not be used in subjects with a history of hypercoagulability (e.g., deep vein thrombosis, pulmonary embolism);
    - ii) Abstinence from penile-vaginal intercourse when this is the subject's preferred and usual lifestyle;
    - iii) Intrauterine device or intrauterine system;
    - iv) Male partner sterilization at least 6 months prior to the female subject's entry into the study, and this male is the sole partner for that subject.
9. Has normal screening electrocardiogram (ECG) or screening ECG with no clinically significant findings as judged by the Investigator.

Exclusion:

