## 2.3 EXPLORATORY OBJECTIVES AND ASSOCIATED ENDPOINTS

Exploratory Objectives	Associated Exploratory Endpoints
1. Describe the efficacy of VGX-3100, administered alone or in combination with imiquimod, at Week 74 and/or Week 96 as measured by reduction in the surface area of the qualifying  vulvar lesion(s), in subjects without a complete resolution at Week 48	1. Percent reduction in the cumulative surface area of the acetowhite vulvar lesion(s) as determined by the quantitative analysis of standardized pre-biopsy photographic imaging of the qualifying  lesion (s) at Week 74 and/or Week 96 compared to baseline  . Results will be classified as: no clinically significant lesion resolution (reduction in lesion area of 0-25%), partial lesion area resolution (>25% and <100% reduction), and complete lesion resolution (no visible lesion).
2. Describe the efficacy of 5 or 6 doses of VGX-3100, alone or in combination with prior imiquimod, as measured by histologic regression of vulvar HSIL	2. Proportion of subjects with no evidence of vulvar HSIL on histology (i.e. biopsies or excisional treatment) at Week 74 for subjects who receive 5 doses of VGX-3100 and at Week 96 for subjects who receive 6 doses of VGX-3100.
3. Describe the efficacy of 5 or 6 doses of VGX-3100, alone or in combination with prior imiquimod, as measured by virologic clearance of HPV-16/18	3. Proportion of subjects with no evidence of HPV-16/18 in vulvar tissue samples at Week 74 and/or Week 96.
4. Evaluate tissue immune responses to VGX-3100, and VGX-3100 with imiquimod, as measured in vulvar tissue samples	4. Assessment of pro-inflammatory and immunosuppressive elements in tissue 
5. Describe virologic clearance of HPV-16/18 from non-vulvar anatomic locations	5. Proportion of subjects who have cleared HPV-16/18 on specimens from non-vulvar anatomic locations without surgical intervention (inclusive of cervix, oropharynx, vagina and intra-anus) at Week 48 compared to baseline
6. Characterize HLA haplotypes and the correlation with efficacy	6. Proportion of subjects with regression of HSIL on histology (i.e. biopsies or excisional treatment) at Week 48 visit

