7. Describe association of microRNA (miRNA) profile, previous vulvoscopy, and HPV testing results with Week 48 histologic regression	7. Vulvoscopy, HPV test results (vulvar swab and vulvar tissue) and miRNA profile (Day 0, Week 15 and 48) in conjunction with histologic regression of vulvar HSIL at Week 48 visit
8. Describe patient reported outcomes (PRO) for subjects treated with VGX-3100 and VGX-3100 with imiquimod	8. PRO endpoints will be obtained at Day 0 prior to first dose, Weeks 4, 12, 24 after dosing, and at Weeks 15, 27, 48, 52, 74, 96 and 100.

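### Section 8.9 analyses the exploratory HLA, miRNA, vulvoscopy and HPV results against the primary composite, but Section 2.3 names Week 48 histologic regression; for Week 48 tissue HPV the composite makes the association circular

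*Protocol*

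**What the plan says.** Section 8.9 plans an exploratory analysis of the "relationship between the primary efficacy endpoint and a) HLA results, b) miRNA results, c) vulvoscopy results, and d) HPV results". The tools are contingency tables and/or "logistic regression models which model the primary endpoint versus these results and treatment group as regressor variables". No HPV specimen or time point is named.

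Section 2.1 defines the primary endpoint as "Proportion of subjects with no histologic evidence of vulvar HSIL and no evidence of HPV-16/18 at Week 48 in vulvar tissue samples". Table 3 in Section 3.2.1 classes as a non-responder any "Subject with evidence of HPV-16 or HPV-18 in vulvar tissue at evaluation".

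Section 2.3 names a different outcome. Objective 7 is to "Describe association of microRNA (miRNA) profile, previous vulvoscopy, and HPV testing results with Week 48 histologic regression", and its endpoint takes vulvoscopy, HPV results from swab and tissue, and miRNA at Day 0, Week 15 and Week 48 "in conjunction with histologic regression of vulvar HSIL at Week 48 visit". The endpoint for HLA (number 6) is "Proportion of subjects with regression of HSIL on histology (i.e. biopsies or excisional treatment) at Week 48 visit". Section 3.4 likewise speaks of HLA type and regression.

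On versions: Section 8.9 is shown for Version 2.0, and Version 1.3 carries the same outcome. Section 8 of Version 2.1 is not in the text at hand. The Version 2.1 list of changes from Version 1.3 names only Sections 8.3 and 8.8 within Section 8, and exploratory endpoints 6 and 7 read the same in Versions 2.0 and 2.1.

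**The concern.** There are two separate problems.

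First, the analysis section and the objectives disagree on the outcome. An analyst who follows Section 8.9 does not answer exploratory objective 7 or report exploratory endpoint 6. One who follows Section 2.3 departs from Section 8.9. This affects all four predictors, not only HPV.

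Second, the composite contains tissue HPV clearance at Week 48. Section 8.9 lists HPV results as a predictor of that composite, and endpoint 7 includes vulvar tissue among them without excluding Week 48. If Week 48 tissue status is used, part of the outcome is related to the whole. The result would look like near-perfect prediction and say nothing about biology.

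At stake is what the exploratory work can claim. Section 6.9 describes the miRNA profiling as a step towards an algorithm to predict treatment success, so the outcome being predicted must be unambiguous.

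**Working it through.** The protocol gives no figure for these analyses, so there is none to reproduce. The check sets the definitions side by side and then asks what a fitted model would do.

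**Step 1: where the two outcomes differ.** Classify women by Week 48 histology and tissue HPV-16/18, leaving non-study treatment aside:

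| Histology | Tissue HPV-16/18 | Section 2.3 (histologic regression) | Section 8.9 (composite) |
|---|---|---|---|
| No HSIL | Not detected | Event | Event |
| No HSIL | Detected | Event | Non-event |
| HSIL | Not detected | Non-event | Non-event |
| HSIL | Detected | Non-event | Non-event |

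The outcomes differ in the second row. Every composite responder is also a histologic regressor, so regression has at least as many events.

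**Step 2: which tissue results can vary.** Section 6.12 places tissue genotyping at Screening and Weeks 48, 74 and 96. Eligibility requires "Vulvar infection with HPV types 16 and/or 18 confirmed by screening biopsy". So HPV-16/18 positive-or-negative status in tissue is the same for every woman at Screening and first varies at Week 48, where it is a component of the endpoint. Genotype at Screening is another matter: type 16, type 18, both, and additional types can all occur (Section 6.1.1).

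**Step 3: Week 48 tissue status against the composite.** By Table 3, P(responder | HPV-16/18 positive in tissue at Week 48) = 0. The positive/responder cell is therefore empty in any data set. Simulation with 22 + 11 evaluable women and response rates of 20% and 28% confirmed this. The cell was empty in all 20,000 simulated trials at each of three assumed rates of clearance without response (5%, 10%, 20%; these rates are assumptions, as the documents give none).

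One simulated trial gave:

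| Week 48 tissue HPV-16/18 | Responder | Non-responder |
|---|---|---|
| Cleared | 9 | 2 |
| Positive | 0 | 22 |

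The odds ratio is (9 x 22) / (2 x 0), which is infinite. A logistic fit on clearance and arm gave these values for the clearance coefficient:

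| Iterations | Coefficient | Standard error |
|---|---|---|
| 10 | 12.8 | 57 |
| 25 | 25.7 | about 35,500 |
| 50 | 35.4 | about 4.6 million |

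No finite maximum-likelihood estimate exists. The separation is quasi-complete: cleared women appear in both outcome columns, positive women in only one.

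**Step 4: the same predictor against histologic regression.** The cell for positive women who regressed is not empty by definition, so the association can be described. Its size cannot be computed in advance, because no rate for regression alone is given.

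**Step 5: how sparse the data are.** Section 8.3 assumes 90% evaluable: 24 x 0.90 = 21.6, about 22, and 12 x 0.90 = 10.8, about 11. Expected composite responders: 22 x 0.20 + 11 x 0.28 = 4.40 + 3.08 = 7.48, about 7.5 of 33.

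**The case against.** The strongest reply is that circularity is a worst-case reading. Section 8.9 says only HPV results. Vulvar swabs are taken at Day 0 and Weeks 4, 12 and 27, cervical samples at Day 0 and Week 12, and tissue is genotyped at Screening. All of these precede the endpoint and none is part of it. Section 8.9 also allows contingency tables, so no failing regression is mandated. The choice of specimens and time points could be left to a statistical analysis plan, which is not shown. And the work is exploratory.

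Much of this stands. A reader might infer that every HPV predictor is circular, or that no other tissue result can vary. The documents do not support that: screening genotype and earlier swabs are legitimate predictors. Nor is the separation complete, since a woman can clear HPV and still have HSIL. Penalised or exact estimation, and fitting one predictor at a time, are matters for the analysis plan; leaving them out is not an error here.

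Two things are not answered. The outcome mismatch is not an omission: Section 8.9 states one outcome and Section 2.3 another, and an analysis plan cannot follow both in a single analysis. And choosing the contingency table does not rescue Week 48 tissue HPV against the composite, because one cell of that table is fixed in advance.

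**Conclusion.** Wrong as written. Section 8.9 names the composite as the outcome of analyses whose endpoints in Section 2.3 are histologic regression. This mismatch rests on the text alone. The circularity is conditional: it arises if Week 48 tissue HPV-16/18 status is related to the composite, which endpoint 7 does not exclude. In that case it is certain, with an empty cell and no finite odds ratio.

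The consequence is confined to exploratory results. A reader might infer that the primary test or the power statement is compromised; neither uses these models. A reader might also infer a known loss of events for HLA and miRNA. The documents show only that histologic regression has no fewer events than the roughly 7.5 expected composite responders; how many more cannot be said.

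The conclusion assumes that Section 8.9 of Version 2.1 reads as in Version 2.0, which the list of changes supports but which cannot be checked directly.

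**What to change.** In Section 8.9, change the outcome of the exploratory HLA, miRNA, vulvoscopy and HPV analyses to histologic regression at Week 48, as in Section 2.3. Name the HPV specimens and time points used as predictors; screening genotype and swabs taken before Week 48 can stay. Show Week 48 tissue HPV against histology as a descriptive cross-tabulation. If the composite is kept as an additional outcome, exclude Week 48 tissue HPV as a regressor for it.

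Do not limit all predictors to those measured before Week 48. Endpoint 7 requires miRNA at Week 48, which should remain and be reported as a concurrent association, not as prediction.

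The cost is a wording change. It needs no new data and has no effect on conduct, sample size or the primary analysis.

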## 8.10 IMMUNOGENICITY ANALYSIS

Post-baseline cellular and humoral response magnitude will be summarized with medians and associated non-parametric 95% CIs. Post-baseline tissue response magnitude will be summarized with means and associated t-distribution based 95% CIs.

Valid samples for statistical analysis purposes will be those collected within 7 or 14 days of the specified time points (see [Table 1](#)). Baseline is defined as the last measurement prior to the first treatment administration.

## **8.11 SAFETY ANALYSES**

### **8.11.1 ADVERSE EVENTS**

All AEs will be summarized among the safety population by frequency per treatment arm. These frequencies will be presented overall and separately by dose, and will depict overall, by system organ class and by preferred term, the percentage of subjects affected. Additional frequencies will be presented with respect to maximum severity and to strongest relationship to Study Treatment. Multiple occurrences of the same AE will be counted only once following a worst-case approach with respect to severity and relationship to Study Treatment. All serious AEs will also be summarized as above.

The main summary of safety data will be based on events occurring within 14 days of any dose. For this summary, the frequency of preferred term events will be summarized with percentages and exact Clopper-Pearson 95% confidence intervals. Separate summaries will be based on events occurring within 7 days of any dose and regardless of when they occurred.

Any AEs with a missing or partial onset date will be included in the overall AEs, but not be included within specified day-range summaries. AE duration will be calculated as (Stop Date – Start Date) + 1.

### **8.11.2 LABORATORY DATA**

Continuous response variables per time point and changes from baseline will be summarized with mean, median, minimum, and maximum values, and categorical response variables will be summarized per time point with percentages, by treatment arm. Baseline is defined as the last measurement prior to the first treatment administration.

### **8.11.3 VITAL SIGNS**

Measurements for vital signs as well as changes from baseline will be summarized with descriptive statistics: mean standard deviation, minimum, median, and maximum values by time point and treatment arm, for the mITT population. Baseline is defined as the last measurement prior to the first treatment administration.

### **8.11.4 PHYSICAL EXAMINATION**

The percentage of subjects with abnormal physical examination findings at each time point will be summarized by treatment arm and by body system, for the mITT population.

### **8.11.5 PATIENT REPORTED OUTCOMES**

As an exploratory endpoint, patient reported outcomes will be summarized with medians or proportions of subjects with endpoints and associated non-parametric or exact Clopper-Pearson 95% CIs, for continuous responses and binary responses, respectively.

### **8.11.6 MISSING VALUES**

Missing data will not be imputed or replaced, and calculations will be done on reported values.

### **8.11.7 INTERIM ANALYSIS**

No formal interim analyses will be performed for this study.

## **9. ETHICS**

### **9.1 INVESTIGATOR AND SPONSOR RESPONSIBILITIES**

The Investigator and Sponsor are responsible for ensuring that the clinical study is performed in accordance with the protocol, the Declaration of Helsinki, principles of Good Clinical Practice (GCP), and applicable regulatory requirements.

### **9.2 INSTITUTIONAL REVIEW BOARD OR ETHICS COMMITTEE (IRB/EC)**

The Investigator will undertake the study after full approval of the protocol and adjunctive materials (e.g., informed consent form, advertising) has been obtained from the applicable IRB/EC and a copy of this approval has been received by the sponsor.

Investigator responsibilities relevant to the IRB include the following:

- During the conduct of the study, submit progress reports to the IRB/EC as required.
- Notify the Sponsor immediately of any SAEs or serious unanticipated adverse device effects.
- If Sponsor notifies you about any reportable safety events notify the IRB immediately.
- As required, obtain approval from the IRB/EC for protocol amendments and for revisions to the consent form or subject recruitment advertisements;
- Reports on, and reviews of, the trial and its progress will be submitted to the IRB by the Investigator at intervals stipulated in their guidelines and in accordance with pertinent regulations and guidelines.
- Maintain a file of study-related information that includes all correspondence with the IRB;
- Notify IRB when study is completed (i.e. after the last study visit of the final study subject);
- After study completion provide the IRB with a final report on the study.

### **9.3 OFFICE OF BIOTECHNOLOGY ACTIVITIES (OBA)**

The Investigator and Sponsor are responsible for ensuring that the clinical study is reviewed and approved according to local and applicable global regulations (e.g., NIH Office of Biotechnology Activities) governing research that involves recombinant or synthetic nucleic acid molecules.

### **9.4 COMPLIANCE WITH INFORMED CONSENT REGULATIONS**

Written informed consent is to be obtained from each subject prior to Screening into the study, and/or from the subject's legally authorized representative. The process for obtaining informed consent must also be documented in the subject's medical record.

### **9.5 COMPLIANCE WITH IRB/EC REQUIREMENTS**

This study is to be conducted in accordance with applicable IRB/EC regulations. The Investigator must obtain approval from a properly constituted IRB/EC prior to initiating the study and re-approval or review at least annually. Sponsor is to be notified immediately if the responsible IRB/EC has been disqualified or if proceedings leading to disqualification have begun. Copies of all IRB/EC correspondence with the Investigator must be provided to Sponsor.

